5.10.5 Economic evaluations

We will conduct an economic evaluation alongside the clinical trial from the perspective of NHS and social services. Additionally, we will collect information on other relevant resource use (e.g. use of the criminal justice system) to enable a broader social perspective to be estimated. The economic analyses will compare the SOTSEC-ID intervention to the TAU group, using two different outcome measures. The first and main health economic analysis will be a cost-utility study. We will estimate quality adjusted life years (QALYs), estimated using the EQ-5D-5L. The EQ-5D-5L will be obtained from participant self-report at baseline, 8-months, 12, months, and 24 months. QALYs will be estimated using the 'area under the curve' method assuming straight line interpolation between

observations. In the second analysis, we will estimate cost-effectiveness using the primary outcome measure, QACSO, and will estimate the cost per one-point improvement in the QACSO. The time frame of the analysis will be the same as the clinical trial, i.e., 2-years. We will perform a 'within-trial' analysis. As the trial has a duration of more than 1-year we will follow national guidance on discounting to allow for the differential weighting of costs and benefits in different time periods (NICE guidelines).

One important output of the trial will be an estimate of the costs required to provide the SOTSEC-ID intervention. This will comprise the following key components. Firstly, the SOTSEC-ID requires a 3-day training course. We will record all attendance by staff at this training to estimate staff time required. Additionally, details of staff required to provide the training will be recorded, as well as details of any consumables. Secondly, a record will be kept of the group CBT sessions provided. This will include attendance so that average numbers attending and hence a cost per attendance can be calculated. A record will be kept of the staff providing the intervention. Details will be recorded of the staff type in attendance, and, if possible, the agenda for change (AfC) band of these health care professionals. We will also ask staff to estimate any travel time required to provide the sessions. Sessions would typically be 2-hours long and there would be 50 sessions in total. Thirdly, details will be collected of the 3 sessions with the participant's carer. Again, staff required to provide these sessions will be recorded. Fourthly, after the conclusion of the intervention participants will receive 6-weekly follow-up sessions. Again, attendance and staff required to provide these sessions will be recorded.

In addition to the resources described above, we will additionally record health and social care provided to allow an estimate of the cost of health and social care resources utilised by the two study groups. This will also quantify what represents TAU in the control group. As this is a pragmatic cluster randomised trial, TAU may vary between sites included in the study. Relevant resource use will be collected using a modified Client Services Receipt Inventory (CSRI), in which it will be noted if the man's notes and records have been consulted to aid its completion. The CSRI will be completed by means of a face-to-face interview, ideally including the participant themselves, along with a family or professional carer. As recall will be important in this process, we will use a recall period of 12-weeks for data collection. The exception to this will be use of prescribed medicines where a recall period of 4-weeks will be used as these may be complex and pose a high burden on those completing the form. The CSRI also includes relevant resource use outside the health and social care sector: for example, contacts with the criminal justice system. All resources identified will be costed using appropriate unit cost data, for example the NHS reference costs (National Cost Collection for the NHS. NHS. Accessed at: NHS England » National Cost Collection for the NHS) and Unit Costs of Health and Social Care (PSSRU, https://doi.org/10.22024/UniKent/01.02.84818). We will use the most up to date available unit cost data at the time of analysis.

5.10.5.1 Health Economic Analysis Plan

In accordance with NCTU practice we will draft a health economic analysis plan (HEAP) prior to conducting the economic analysis. This will be shared and discussed with members of the TMG and other key personnel before analysis is undertaken. Where there is a discrepancy between the HEAP and the protocol, the HEAP will have priority.

5.10.5.2 Within-trial analysis

The analysis will adopt a 'within trial' approach, i.e., up to the two-year follow-up point of the clinical trial. In line with the statistical analysis, we will analyse patterns of missing data, and where appropriate, multiple imputation will be used to impute data. Decisions relating to the treatment of missing data will be made in consultation with the study CI and statistician. If data is imputed then results will be presented for both the imputed data as well as a complete case analysis (CCA). Data will be analysed on an intention to treat basis. Costs and effects will be analysed using regression-based methods to allow for any differences in baseline characteristics (mindful of the prognostic variables identified and used in the SAP). Incremental costs and effects will be reported. Additionally, if one group is more costly and more effective than the other, we will report incremental cost-effectiveness ratios (ICERs). Non-parametric bootstrapping will be used to analyse uncertainty. Uncertainty inherent in the data will be represented by means of a cost-effectiveness acceptability curve (CEAC). Analyses will be performed in a variety of packages, these are likely to include: MS Excel SPSS; R; and STATA.

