5.7 Sample Size

In our previous single group study, of 109 participants, the magnitude of change following treatment in the primary outcome measure, the QACSO, was 22.5 (SD = 24), and the observed ICC was 0.15 (Murphy, Sinclair, Melvin & Langdon, 2023). Assuming a similar change in the intervention group in this new study and a change of no more than one fifth of this in the controls (it is unlikely to be greater given the lack of CBT intervention in this group directed at sexual behaviour), we would expect a mean difference of around 18 units in the QACSO between the two groups. This led to a proposed sample size of 164 in our first Stage 2 submission to NIHR. However, this was considered by the HTA panel to be relying on too large an expected effect size, i.e. one of 0.75 standard deviations, and consequently running the risk of an inflated Type II error. We have, therefore, revised our calculations considering smaller effect sizes. We now propose using 30 sites and a total target sample size of 240. Under the same assumptions (ICC = 0.15 and an attrition rate of 20%), this would provide statistical power of 90% for an effect size of 0.607 and 80% for an effect size of 0.525. These would translate into 14.5 and 12.6 units difference on the QASCO. In our experience in our previous studies, attrition is less than 20% and, we believe the risk of a Type II is now well mitigated against.

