5.9 Assignment of Intervention

The trial is a cluster-randomised controlled trial.

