5.9.1 Allocation

5.9.1.1 Sequence generation -

Participating sites will be randomly allocated to either the group CBT programme or treatment as usual with a 1:1 ratio of allocation. Allocation will occur after site eligibility has been established and in two tranches: the first 10 sites will comprise the pilot phase, the remaining 20 will be allocated after month 13. Sites will be randomly allocated instantaneously, 5 in each group for the pilot, and 10 to each group for the remaining trial period. Random allocation will be the responsibility of Norwich CTU. The staff responsible will be blinded to site identity.

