5.10.4 Statistical Methods

5.10.4.1 Outcomes

The primary outcome measure will be the Questionnaire on Attitudes Consistent with Sexual Offending (QACSO) score. Secondary outcome measures are the further occurrences of harmful sexual behaviour, sexual knowledge scores, victim empathy scores, locus of control and self-esteem scores.

The EQ-5D-5L will also be completed for health economics purposes. These measures at baselines, 8 months, 12 months and 24 months will be captured using the same instruments (see Table page 26).

The primary efficacy analysis will be of the QACSO at 12 months. A general linear model with baseline QACSO as a covariate will be used as the primary means of analysis. Allocated treatment group will be included as a fixed effect. Due to randomisation being at the site level, rather than the individual level, generalised estimating equations (GEEs) will be used for parameter estimation to adjust for correlations between participants within sites. All estimates will be provided with 95% confidence intervals. Additional prognostic variables will be included in the analytical model as specified prior to any analysis, in the statistical analysis plan. Statistical significance will be set at the two-sided 5% level. All secondary outcomes will be analysed in an analogous manner.

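### The economic evaluation names regression, bootstrapping and a CEAC without any allowance for site, although sites are the unit of randomisation

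*Protocol*

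**What the plan says.** On design, section 5.9 states: "The trial is a cluster-randomised controlled trial". Section 5.7 gives the size: "We now propose using 30 sites and a total target sample size of 240". Section 5.9.1.1 allocates sites "with a 1:1 ratio of allocation", so there are 15 sites per arm.

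For efficacy, section 5.10.4.1 gives site-level randomisation as the reason that "generalised estimating equations (GEEs) will be used for parameter estimation to adjust for correlations between participants within sites".

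For economics, section 5.10.5.2 says: "Costs and effects will be analysed using regression-based methods to allow for any differences in baseline characteristics". It then says "Non-parametric bootstrapping will be used to analyse uncertainty" and plans to show uncertainty as a CEAC. It takes its approach to missing data from the statistical analysis and its prognostic variables from the SAP. It mentions neither site, nor clustering, nor the unit to be resampled.

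Two neighbouring sections bear on this. Section 5.10.5 recognises that the trial is cluster randomised and that usual care can differ from site to site. Section 5.10.5.1 promises a HEAP before the economic analysis and gives it precedence over the Protocol where the two differ.

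**The concern.** The Protocol treats within-site correlation as something to settle at protocol level for efficacy, and then leaves it out when it names the economic methods. A non-parametric bootstrap run without further instruction normally resamples individuals. In a cluster-randomised trial that treats men from the same site as independent and understates the variance of the incremental cost, the incremental QALYs and the net benefit. The CEAC is built from the same draws, so it would be pushed towards 0 or 1 and would look more decisive than 30 randomised units allow.

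The Protocol gives reasons to expect costs to cluster. Intervention cost arises at group level: attendance, staff mix and travel are largely shared within a group (5.10.5). Settings run from community teams to medium secure units (5.1.1), and secure places are put at £150,000 to £200,000 a year (4.1). Usual care differs between sites (5.10.5). Some groups mix legally restricted and unrestricted men (5.1.1), which weakens the link between site and cost without removing it. For QALYs the Protocol gives no indication either way.

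**Working it through.** **The plan's own clustering figure.** The Protocol gives no ICC, interval width or CEAC value for the economic outcomes. Its only clustering figure is the power statement in 5.7, "statistical power of 90% for an effect size of 0.607 and 80% for an effect size of 0.525", at ICC 0.15 with 20% attrition.

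- All 240 men analysed: 240/30 = 8 per site; design effect 1 + (8 − 1) × 0.15 = 2.05; effective size 120/2.05 ≈ 58 per arm. A two-sample t-test then detects 0.525 SD at 80% power and 0.607 SD at 90%, which matches.
- 20% attrition deducted: 192 men, 6.4 per site, design effect 1.81, effective size 96/1.81 ≈ 53 per arm. Power is 77.1% at 0.525 and 87.8% at 0.607 (normal approximation).

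The stated figures therefore match only without the attrition deduction. That is a separate matter and does not affect this point. It does confirm the cluster structure to use below.

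**Inputs.** 30 sites, 15 per arm; 240 × 0.8 = 192 men analysed; m = 192/30 = 6.4 per site. The ICC for costs and QALYs is an assumption, shown as a range. The value 0.15 is borrowed from the QACSO.

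**Formulas.** Design effect DE = 1 + (m − 1) × ICC. If site is ignored, interval width relative to the correct width is 1/√DE, and nominal 95% coverage is 2Φ(1.96/√DE) − 1.

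| Assumed ICC | DE | Relative width | Coverage by formula |
|---|---|---|---|
| 0.01 | 1 + 5.4 × 0.01 = 1.054 | 0.97 | 94% |
| 0.05 | 1 + 5.4 × 0.05 = 1.27 | 0.89 | 92% |
| 0.10 | 1 + 5.4 × 0.10 = 1.54 | 0.81 | 89% |
| 0.15 | 1 + 5.4 × 0.15 = 1.81 | 0.74 | 86% |

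With no attrition (m = 8) and ICC 0.15, DE = 2.05, relative width is 0.70 and coverage 83%.

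**Simulation check.** Percentile bootstrap of a difference in means, 15 sites per arm, no covariates. Setting A has Binomial(8, 0.8) men per site, 1,500 trials and 400 draws. Setting B has 6 or 7 men per site (192 in all), 1,000 trials and 300 draws.

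| ICC | Men resampled, A | Men resampled, B | Sites resampled, A | Sites resampled, B |
|---|---|---|---|---|
| 0.01 | – | 93.0% | – | 91.5% |
| 0.05 | 90.3% | 91.0% | 92.7% | 92.3% |
| 0.15 | 85.2% | 85.7% | 92.5% | 92.6% |

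Monte Carlo error is about 1 percentage point. Two things follow. Resampling men loses coverage as the ICC rises, in line with the formula. Resampling whole sites holds coverage at about 92–93%, a little short of 95% because 15 sites per arm is few; at ICC 0.01 it brings no gain in coverage.

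**The case against.** The strongest reply is that 5.10.5.2 is silent rather than wrong. A bootstrap that resamples sites is also non-parametric, and regression can include a site effect or cluster-robust errors, so a correct analysis would contradict nothing in the text. The HEAP is the natural place for such detail and overrides the Protocol. The economic text shows awareness of the cluster design. Section 5.10.4.1 also says the secondary outcomes are handled like the primary one, and sections 1.3 and 5.5.2 list the CSRI and EQ-5D-5L among them.

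Much of this stands. A reader might infer that the Protocol commits to an individual-level bootstrap, or that the economic intervals are bound to be too narrow. The text supports neither: the resampling unit is not stated, a HEAP is still to come, and no ICC for costs or QALYs is given. Baseline covariates could also absorb part of the between-site variation, so the relevant ICC is the residual one.

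The reply does not remove the point. The list of secondary outcomes in 5.10.4.1 itself leaves out costs and sets the EQ-5D-5L apart for economic use, so the carry-over is doubtful, and it would not reach the bootstrap in any case. The HEAP's precedence helps only if the HEAP departs from 5.10.5.2, and nothing requires that. The SAP must be produced before data collection ends, with approval sought from the oversight committees (5.10.4.2). The HEAP need only be drafted before the economic analysis and discussed with the trial management group and other key personnel.

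**Conclusion.** The point holds in a conditional form. Section 5.10.5.2 names its methods without any allowance for the unit of randomisation, while 5.10.4.1 makes that allowance for efficacy. If the bootstrap is run in the usual way on individual men, uncertainty is understated for any positive ICC. With 6.4 men per site the shortfall in interval width runs from about 3% at ICC 0.01 to 26% at 0.15, and nominal 95% coverage from about 94% down to 85–86%. These figures assume near-equal site sizes, 20% attrition and no covariate adjustment. The ICC values are assumptions, and 0.15 belongs to the QACSO. The direction is firm; the size is not known. Because cost-utility is the main economic analysis (5.10.5), this deserves settling before outcome data are analysed.

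**What to change.** Add to 5.10.5.2, and carry into the HEAP, that:

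- the cost and QALY regressions account for site, for example by a multilevel model or by GEE with a small-sample correction;
- bootstrap samples are drawn by site within arm, and the CEAC is built from those draws;
- any multiple imputation respects the site structure.

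The exact multilevel model, and whether to use a shrinkage correction for the small number of sites, can be left to the HEAP. The slight under-coverage of a simple site bootstrap with 15 sites per arm is a reason to address that correction there. The cost is a few sentences, a little more programming and wider intervals. No change to data collection is needed.

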5.11 Data Monitoring

5.11.1 Data Monitoring Committee

Further details of the roles and responsibilities of the Data Monitoring Committee (DMC), including membership, relationships with other committees, decision making processes, and the timing and frequency of interim analyses (and description of stopping rules and/or guidelines where applicable) are described in detail in the HASB-IDD DMC Terms of Reference (ToR).

5.11.2 Interim Analyses

No formal interim data analyses are planned. All analyses for the Data Monitoring Committee will be descriptive in nature rather than inferential. The DMC may, however, require formal interim analyses be conducted when necessary. Any such analyses will be described in writing and agreed with the DMC before being conducted.

5.11.3 Data Monitoring for Harm

Adverse events (AEs) and Serious Adverse Events will not be collected in this trial. Instead, incidences of harmful behaviour will be collected at each time point, using the Harmful Behaviour Schedule. Incidences will be reviewed cumulatively by the DMC over the duration of the trial. As incidences of harmful behaviour are recorded retrospectively at baseline, 8, 12 and 24 months, it is not possible for researchers to act upon the information received or indeed to influence the outcome of the incident. As such, the Trial team are not responsible for following up on any events.

Carers will be required to notify social workers and police, where necessary, where the incidences warrant it.

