Self-Esteem: for the men themselves, it is important to assist them to maintain their own self-esteem, which is often very low, at the start of treatment. At times, the intervention may threaten their self-esteem, partly because it helps them understand their responsibility for their behaviour. At other points the intervention will help them build their self-esteem, by recognizing how they are progressing towards 'good lives'. It is known that self-esteem correlates with good mental health so it is important to be sure that overall self-esteem rises with treatment, rather than falls, and for this reason a well-established measure of self-esteem adapted for people with IDD and with good psychometric properties (Dagnan & Sandhu, 1999; Keeling et al, 2007) will also be used at all time points.

Harmful Sexual Behaviour Schedule: Incidences of harmful sexual behaviour that have occurred during the 5 years prior to baseline, and then between baseline and 8 months, 8 and 12 months and 12 and 24 months will be recorded at baseline, 8, 12 and 24 month follow-up time points, respectively, using information from patient and carer report, case notes, police interviews, court appearances, and court convictions. Research assistants will report such incidents to the local clinician. Clinicians/professionals working with the participants have a responsibility and duty of care to report any safeguarding concerns or crimes, including sexual abuse, to the relevant authoritative body (local Safeguarding Board), when they are made aware of these during the trial.

5.5.2.2 Heath Economic Outcome Measures:

Client Services Receipt Inventory (CSRI): Use of health, social and CJS resources used by participants will be collected from a modified CSRI completed with participants and/or their carers; this will allow the cost of service use to be estimated. The CSRI will note if responses have been informed by reference to notes/records. Information about input from the MDT team (Q6c) at all timepoints will be collected by the Trial Managers from a delegated person in the site team. This is to protect the Research Assistants from becoming unblinded.

The EuroQol quality of life measure, EQ-5D-5L, a validated quality of life measure comprising of five questions or dimensions and a visual analogue scale will be completed to evaluate changes in quality of life.

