5.6.1 Participant Assessments

Participants' assessments will normally take place in their Community Team offices or in the secure unit, if they are detained there. Occasionally they may take place in the man's place of residence (but only if staff are present). They will be told they may bring a carer if they wish (family carer or paid carer). In our experience most men will wish to do this, as they are frequently anxious about

meeting new people (in this case the research assistant). Typically the men will ask the carer to stay for a bit, while they get comfortable with the setting and RA, and then the carer is usually able to wait outside in the waiting room. In some cases it may be necessary to conduct assessments using a web-based meeting platform (for example in the event of further restrictions due to Covid-19), though this would not be routinely offered. The men can have a carer present with them if they need support to access the web-based meeting and for other support.

The assessments on time 1, 2, 3, and 4 will take between 1 and 1.5 hours. Some men will want to do these without stopping. Some will want breaks. It will made clear to them that they may have breaks if they wish. It is anticipated that, if accompanied by a carer, it will be possible to complete the carer assessments (see Table above) after seeing each man, while the man, in turn, waits in the waiting room. Assessments are anticipated to take approximately an hour, although where short breaks are required, they may take longer; they will still be completed within one day where possible.

Research Assistants are expected to comply with local safeguarding procedures and risk assessments when undertaking assessments and interviews.

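### Section 5.11.3 says researchers cannot act on harmful sexual behaviour they learn of, which contradicts the reporting step that 5.5.2.1 gives research assistants

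*Protocol*

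**What the plan says.** Section 5.11.3 (Data Monitoring for Harm) replaces conventional safety reporting with the record of harmful behaviour: "Adverse events (AEs) and Serious Adverse Events will not be collected in this trial". Incidents are gathered at baseline, 8, 12 and 24 months and reviewed cumulatively by the Data Monitoring Committee. Because the recording is retrospective, the section says "it is not possible for researchers to act upon the information received or indeed to influence the outcome of the incident", and it infers: "As such, the Trial team are not responsible for following up on any events". It then names one outside route: "Carers will be required to notify social workers and police, where necessary, where the incidences warrant it".

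Section 5.5.2.1 (Clinical outcome measures) describes the Harmful Sexual Behaviour Schedule at the same four time points, completed "using information from patient and carer report, case notes, police interviews, court appearances, and court convictions". It gives the research assistant a task: "Research assistants will report such incidents to the local clinician". It then describes the next link: "Clinicians/professionals working with the participants have a responsibility and duty of care to report any safeguarding concerns or crimes, including sexual abuse". That duty is owed to the relevant body (the local Safeguarding Board is named) and arises once they learn of the matter during the trial.

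Section 5.6.1 (Participant Assessments) adds: "Research Assistants are expected to comply with local safeguarding procedures and risk assessments when undertaking assessments and interviews".

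**The concern.** Two sections tell the same staff different things about the same information. One gives them a reporting step. The other says that they cannot act on what they hear and that their team has no responsibility to follow it up.

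The reason given in 5.11.3 does not support its conclusion. Retrospective recording means that nobody can change an incident that has already happened. It does not stop a research assistant from telling a clinician about it, and 5.5.2.1 requires exactly that.

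The stakes come from the protocol's own account. Section 4.1 lists children among the victims, as well as people with intellectual disabilities who sometimes share facilities with the men. Section 5.3.1 notes that a victim may be unable to report and that professionals or the public may not have told the police. Since adverse events are not collected, 5.11.3 is the section that sets out how harm is monitored, so a wrong premise there matters more than it would elsewhere.

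**Working it through.** No arithmetic applies. The check sets the passages side by side and asks what each requires.

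1. **Same information?** 5.11.3 calls the instrument the Harmful Behaviour Schedule, and 5.5.2.1 calls it the Harmful Sexual Behaviour Schedule. The time points match (baseline, 8, 12 and 24 months) and the protocol describes no second schedule, so I take them to be one instrument.

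2. **Same people?** 5.11.3 speaks of researchers and the trial team. Section 6.5 refers to research assistants as being on the trial team, and 5.9.2 and 5.10.1 describe the data collectors as researchers and trial team members. The disclaimer therefore covers the staff to whom 5.5.2.1 gives the reporting step.

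3. **Compatible instructions?** Telling the local clinician is a way of acting on the information. 5.11.3 says that acting is not possible; 5.5.2.1 directs it. The premise and the instruction cannot both stand.

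4. **Does the disclaimer sentence alone forbid a report?** No. Following up an event can mean tracking it to its outcome, which is different from handing it over. The conflict lies in the premise, and in the disclaimer being drawn from that premise.

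5. **Where could the difference change what happens?** Compare a research assistant who relies on 5.11.3 alone with one who follows 5.5.2.1 and 5.6.1:

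| Who already knows of the incident | Relying on 5.11.3 alone | Following 5.5.2.1 and 5.6.1 |
|---|---|---|
| The local clinician | The clinician's own duty already applies | The same, with a report from the research assistant as well |
| The carer, not the clinician | Carer is expected to notify social workers and police where warranted; no step to the clinician is named | Research assistant reports to the clinician, whose duty then applies |
| Neither | No notification route is named for the incident | Research assistant reports to the clinician, whose duty then applies |

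The third row is where the gap is widest. The clinician's duty depends on being made aware, and the research assistant's report is what makes the clinician aware.

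6. **Can the third row occur?** 5.5.2.1 lists the man's own report as a source, so a disclosure unknown to the carer is foreseeable. Other sections point to narrower sources: 5.3.1.5 says the record comes from the consenting carer, the table in 5.6 lists the carer and case notes, and the summary in 1.3 refers to carers' report. The protocol gives no frequency for incidents known only to research staff.

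7. **Does the carer sentence close the gap?** Only for incidents the carer knows of. Section 5.3.1 describes the carer's role in the trial as supplying the record of behaviour and of resource use, and section 6.5 has carers giving consent as participants. Apart from the single sentence in 5.11.3, I found no text that sets out a notifying duty for carers or says how it would be secured.

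**The case against.** A reader might infer that a site following 5.11.3 would leave known abuse unreported. The documents do not support that, for three reasons.

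- The disclaimer covers researchers and the trial team, not sites. Site clinicians keep the duty described in 5.5.2.1.
- 5.11.3 itself expects carers to notify social workers and the police.
- Not following up is different from not reporting, and nothing in 5.11.3 expressly prohibits a report.

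It can also be said that research assistants have their own instructions. 5.5.2.1 sits in the description of the schedule they complete, and 5.6.1 names them. A missed report requires someone to rely on 5.11.3 and overlook both. Several of the listed sources, such as case notes, police interviews and court records, are already held by services or authorities. The baseline record looks back five years, and for most men a documented history is part of eligibility, so many of those incidents will already be known.

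A reader might also try to size the problem as 240 men × 4 assessments = 960 schedules. That counts planned forms before any attrition and says nothing about how many incidents are at risk.

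All of this stands, and it limits the consequence. It does not remove the contradiction: the protocol still says that staff cannot do what it elsewhere tells them to do.

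**Conclusion.** The contradiction is real and should be corrected. 5.11.3 rests on a premise that 5.5.2.1 shows to be wrong, draws a disclaimer from it, and names only carers as notifiers. It also sits badly with 5.6.1.

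The supportable consequence is limited. A research assistant relying on 5.11.3 alone might not pass on an incident, and the risk is greatest where neither carer nor clinician already knows of it. A missed report is possible, not certain, and its frequency cannot be estimated from the protocol.

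This rests on two assumptions: that the two schedule names refer to one instrument, and that research assistants fall within the researchers and trial team of 5.11.3. The text supports both. No estimate, error rate or power figure is affected.

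**What to change.** Reconcile 5.11.3 with 5.5.2.1 and 5.6.1:

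- Remove or correct the statement that researchers cannot act on the information. If the intended meaning is that they cannot alter a past incident, say only that.
- Limit the follow-up disclaimer, for example to tracking an event to its outcome, so that it cannot be read as cancelling the reporting step.
- Cross-refer to the chain already set out in 5.5.2.1.
- State whether the carer sentence adds to that chain or replaces it.
- Use one name for the schedule in both sections.

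Leave the handling of individual incidents to local procedures; this review proposes no rule for it. A log showing that each hand-over took place would be a useful extra, but it is optional and not needed to resolve the contradiction.

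The cost is one paragraph of amended protocol text, and a matching line in the research assistants' working instructions if these repeat the wording of 5.11.3. No new visits, staff or data items are needed.
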